2.1 Abdominal core stability

Measured by two-way mixed design ANOVA, there are main time effect, group effect and interaction of time and group.

Before training, there is no significant difference between ADIM+BFR group and ADIM group of double leg lowering test, so as after 3 weeks of training. However, ADIM+BFR group shows significant decrease in angle of double leg lowering test after 4 weeks of training and one week after the end of training, which shows better core stability.

ADIM+BFR group shows significant different among timepoints. Compared with baseline, it shows significant decrease after 3,4 weeks of training and one week after the end of training. Furthermore, after 4 weeks of training and one week after the end of training, it shows significant different compared with week 3 and week 4.

2.2 Abdominal strength test

Measured by two-way mixed design ANOVA, there is main time effect but no group effect and interaction of time and group.

Before training, there is no significant difference between ADIM+BFR group and ADIM group of abdominal strength test measured by dynamometer, so as after 3 weeks of training. However, ADIM+BFR group shows significant increase after 4 weeks of training and one week after the end of training, which shows better core strength.

ADIM+BFR group shows significant different among timepoints. Compared with baseline, it shows significant increase after 4 weeks of training and one week after the end of training. Furthermore, after 4 weeks of training and one week after the end training, it shows significant different compared with week 3. ADIM group shows significant different after 4 weeks of training compared with baseline.

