Effects of Blood Flow Restriction Training Combined with Abdominal draw-in Maneuver on Transverse Abdominis Strengthening

CRREC-109-007

Date: 2021/09/14

I. Study Protocol:

Healthy adults (age ranged 18-34 years and BMI between 18.5~24.99) were randomly recruited in the study. For the intervention group, an inflatable cuff (14 cm in width * 84 cm in length) is warped around abdominal muscles below ribs which may cause to at least 60% restriction of blood flow detected by Power Doppler ultrasonography. All participants are instructed to perform ADIM both condition of BFR and BFR-free twice a week, for four weeks. Core muscle thickness will be measured at rest and at draw-in by 2D ultrasound. Abdominal core stability, strength and endurance test by double leg lowering test, dynamometer and abdominal static endurance test.

II. Statistical Analysis Plan

Two-way mixed design ANOVA test is used to measure the group difference, time difference and interaction. Using Bonferroni post hoc test to analyze the difference among timepoints within group and Independent t test for the difference between two groups.

III. Results

1. Muscle thickness measured by ultrasound

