1.1 Transverse abdominis

Measured by two-way mixed design ANOVA, there is no main time effect, group effect and interaction of time and group of mean bilateral thickness of transverse abdominis (TrA) at rest. At draw-in, there is no main time effect but group effect and interaction of time and group of mean bilateral thickness of TrA. Of muscle thickness change between draw-in and resting, there are main time effect, group effect and interaction of time and group of mean bilateral thickness of TrA.

Before training, there is no significant difference between ADIM+BFR group and ADIM group of TrA thickness at rest, draw-in and thickness change(p>0.05). After 3 weeks of training, there is no significant difference between ADIM+BFR group and ADIM group of TrA thickness at rest. ADIM+BFR group shows significant thicker muscle at draw-in and thickness change. After 4 weeks of training, there is no significant difference between ADIM+BFR group and ADIM group of TrA thickness at rest. ADIM+BFR group shows significant thicker muscle at draw-in and thickness change. One week after the end of training, there is no significant difference between ADIM+BFR group and ADIM group of TrA thickness at rest. ADIM+BFR group shows significant thicker muscle at draw-in and thickness change.

ADIM+BFR group shows no significant difference of TrA thickness among timepoints at rest. There is significant increase at week 4 and one week after the

end of training compared with baseline and at week 4 compared with week 3 at draw-in. There is significant thickness change at week 3, 4 and one week after the end of training compared with baseline. There is no significant difference at rest, at draw-in and thickness change among timepoints in ADIM group.

2. Abdominal functional test

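### Section 2.2 claims better core strength for ADIM+BFR beside an ANOVA sentence that most naturally reports a time effect only; the two need reconciling, and superiority on strength is not shown as written

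*Combined protocol and SAP*

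**What the plan says.** Section II (Statistical Analysis Plan) names two procedures that bear on a difference between the groups. The first is the mixed ANOVA: "Two-way mixed design ANOVA test is used to measure the group difference, time difference and interaction". The second is the "Independent t test for the difference between two groups". A Bonferroni post hoc test is planned, but only for timepoints within a group. The SAP does not say which procedure governs if they disagree, does not make the t tests depend on the ANOVA, and states no multiplicity adjustment for them.

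Section 2.2 has three paragraphs on strength:

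- **ANOVA:** "there is main time effect but no group effect and interaction of time and group".
- **Groups at each visit:** no difference before training or at week 3, and then "ADIM+BFR group shows significant increase after 4 weeks of training and one week after the end of training, which shows better core strength".
- **Timepoints within each group:** for ADIM+BFR, "Compared with baseline, it shows significant increase after 4 weeks of training and one week after the end of training"; for the comparator, "ADIM group shows significant different after 4 weeks of training compared with baseline".

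Section 2.2 gives no mean, SD, F statistic, p-value or confidence interval.

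**The concern.** A time effect alone says that strength changed over the study. It does not say that one group did better. If group effect and interaction were both absent, the analysis planned for exactly those questions does not support the superiority claim placed beside it.

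The contrast with the neighbouring sections raises the stakes. Sections 2.1 (stability) and 2.3 (endurance) show the same visit pattern: no difference at baseline or week 3, then a significant change in favour of ADIM+BFR at week 4 and one week after training. Both close with the same form of conclusion, and both report group and interaction effects. Section 2.2 is worded just as firmly without that support. Whether BFR can be said to add to abdominal strength, one of the three functional outcomes, depends on which sentence in 2.2 is right.

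**Working it through.** There is no stated figure to reproduce, so the check is first of wording and then of how often the two statements can coexist.

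**1. What the ANOVA sentence means.** The same list of effects appears in section 1.1. For thickness at rest, "there is no main time effect, group effect and interaction of time and group": one *no* covers the whole list, and the text then reports no differences at rest. For draw-in, "there is no main time effect but group effect and interaction of time and group": what follows *but* covers both group effect and interaction. Where all three effects were found (thickness change in 1.1, and sections 2.1 and 2.3), they are listed with no negation. By this usage, the strength sentence means no group effect and no interaction. That is the natural reading, not a certain one.

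**2. What the claimed increase compares.** It is not labelled.

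- *Between groups.* The layout favours this: in 1.1 and 2.1–2.3, group comparisons come before comparisons among timepoints, and the strength claim follows directly on a statement of no group difference. It would then report the planned t tests.
- *Within group.* It would then repeat the third paragraph. A significant change in one arm is not a comparison of arms, and ADIM alone also differed from baseline at week 4.

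**3. Why the interaction matters most.** Suppose the true difference is d at the last two of four visits and zero before. The group main effect then estimates (0 + 0 + d + d)/4 = d/2, so it can miss a late difference. The interaction tests the late divergence directly, and it is the term whose wording is ambiguous.

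**4. How often the statements coexist on the between-group reading.** All inputs are assumptions: 10–30 per group, four visits, equal correlation 0.5–0.9 between visits, two-sided 0.05. With n per group, the group test is F(1, 2n−2) and the interaction test is F(3, 3(2n−2)). The t-test pattern is: non-significant at baseline and week 3, significant in favour of BFR at both later visits. The useful quantity is

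share = P(pattern, and both ANOVA terms non-significant) / P(pattern).

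Three settings, 10,000 simulated trials each:

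| n per group | correlation | true difference (week 3; later visits) | pattern | pattern, both terms non-significant | share |
|---|---|---|---|---|---|
| 10 | 0.5 | 0.2; 0.7 SD | 12.46% | 1.33% | 1.33/12.46 = 11% |
| 15 | 0.5 | 0.2; 0.7 SD | 22.4% | 1.54% | 1.54/22.4 = 7% |
| 30 | 0.8 | 0.2; 0.7 SD | 55.28% | 0.01% | 0.01/55.28 = 0.02% |

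Over the full assumed range, with the difference confined to the two later visits:

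| true late difference | share with both ANOVA terms non-significant |
|---|---|
| none | about 16–34% |
| 0.3 SD | about 3–20% |
| 0.5–1.0 SD | about 0–13% (up to 15% in repeat runs) |

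**5. Why the joint frequency misleads.** Pattern and null ANOVA together occur in only 0.034–0.055% of trials with no true effect. But the t-test pattern is itself rare there, at about 0.2%: 0.034/0.2 = 17% and 0.055/0.2 = 28%. Most of the rarity comes from the pattern, not from a clash with the ANOVA.

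**6. Multiplicity.** Four unadjusted t tests at 0.05 carry a chance of at least one false positive of 1 − 0.95⁴ = 18.5% if independent. With correlation 0.5–0.8 the simulated figure is about 12–16%.

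**The case against.** The strongest reply is that the t test is itself the planned between-group comparison. The SAP sets no gate, so reporting significant t tests at two visits follows the plan, and treating the ANOVA as decisive is a reviewer's choice. This stands in part. The SAP gives neither procedure priority, and t tests at single visits can be significant when the ANOVA terms are not. It does not rescue an unqualified superiority claim made without estimate, interval, p-value or multiplicity adjustment, beside an ANOVA that appears to say otherwise.

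A second reply is that the sentence was meant as no group effect but an interaction present. That would remove the tension, and it is plausible for a late effect: with true late differences of 0.5–0.8 SD, about 25–65% of trials showing the t-test pattern had a null group effect with a significant interaction. Usage in section 1.1 points the other way but does not settle it, so the output has to be checked before any wording is changed.

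A reader might also infer from the low joint frequencies that one sentence must be misreported. The conditional shares do not support that: with no effect or a small one, the two statements coexist fairly often.

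**Conclusion.** The point holds as a reporting inconsistency that should be fixed. On its natural reading, the ANOVA sentence in 2.2 does not support the superiority claim beside it, and the parallel wording in 2.1 and 2.3 invites equal weight for unequal evidence. Superiority on strength is not shown as written, and it is not disproved.

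The documents do not support two stronger readings. One is that the statements are logically incompatible: they are in tension only. The other is that BFR has no effect on strength: a non-significant term does not show that the groups are equal, and the simulation gives no verdict on BFR because group size, SD, correlation and alpha are all unknown. The conditional shares (about 16–34% with no effect, 3–20% at 0.3 SD, 0–13% at 0.5–1.0 SD) rest wholly on the assumed inputs and on the between-group reading. They justify asking for an explanation and nothing more. The wording evidence carries the point.

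**What to change.** 1. Check the existing ANOVA output for strength and report F, degrees of freedom and p for group, time and interaction.
2. Label the statement about week 4 and one week after training as between-group or within-group.
3. If the interaction was significant, correct the ANOVA sentence.
4. If group and interaction were both non-significant, replace the superiority clause with wording such as: *The mixed ANOVA showed a time effect only; an added effect of BFR on abdominal strength was not shown.* Report any t-test differences beside it, marked as unadjusted for multiplicity.

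Baseline-adjusted between-group differences with confidence intervals at the two later visits would help readers. They are optional, and since results are known they should be marked supplementary.

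The cost is a look at existing output, one label and one corrected sentence; no new data are needed. The downside is that one favourable claim may have to be softened.

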2.3 Abdominal endurance test

Measured by two-way mixed design ANOVA, there are main time effect, group effect and interaction of time and group.

Before training, there is no significant difference between ADIM+BFR group

and ADIM group of abdominal endurance test, so as after 3 weeks of training. However, ADIM+BFR group shows significant increase after 4 weeks of training and one week after the end of training, which shows better core endurance.

ADIM+BFR group shows significant different among timepoints. Compared with baseline and 3 weeks of training, it shows significant increase after 4 weeks of training and one week after the end of training. Furthermore, one week after the end of training, it shows significant different compared with week 3. ADIM group shows significant different after 3,4 weeks of training and one week after the end of training compared with baseline.
